### 8.6.3 Analysis of secondary efficacy endpoint(s)

All analysis of secondary efficacy endpoints will be performed on the ITT population.

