- 2 Only subjects receiving placebo in Study MBGS205 to be randomised. Subjects already on active in Study MBGS205 will maintain their treatment allocation
- 3 All blood samples are to be collected after 8 hours fasting, after ECG and vital sign measurements have been performed
- 4 A microscopic examination including RBC and WBC or urinary protein will be performed only when dipstick evaluation is positive for WBC and/or blood or protein
- 5 Bone turnover markers include CTx1, osteocalcin, bone alkaline phosphatase, and PINP
- 6 Has to be collected before 11 am. If the sample was inadvertently taken after this time, a retest is allowed after a discussion with the Medical Monitor.
- 7 All subjects that are not vasectomised will be asked to provide a semen sample. Subjects that provided semen sample for PK will also have plasma for PK drawn at the assessment visit Semen sample collection is not required to be the same day as the assessment visit. Therefore, semen PK collection is allowed ± 48 hours around the plasma PK attendance visits.
- 8 Subjects should come well hydrated, drinking water the night before and the morning before the impedance measurements
- 9 Activity wrist monitors will be collected from subjects at EOT visit of the Study MBGS205. If the activity wrist monitor was not performed before EOT of Study MBGS205 and collected at EOT Study MBGS205, it can be applied at the Baseline visit of current study and worn for 7 c consecutive days and collected at Visit 2. An activity wrist monitor will also be worn for 7 continuous days after Visit 7 (EOT) and collected at Visit 8 (FU)
- 10 Some questionnaires will be new for some subjects and completed first time at the Baseline visit
- 11 For subjects that discontinued early, EOT DEXA scan will be performed only if they reached minimum Week 36 (Visit 4) active treatment period. In order to accommodate scheduling, EOT DEXA can be performed within 5 days before the EOT visit or 5 days after the EOT Visit
- 12 [REDACTED]
- 13 AEs, SAEs, and AESIs collected from signature of informed consent

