### 4.2 Secondary Endpoints

#### 4.2.1 Secondary Safety Endpoints

1. In subjects that were randomized to active treatment in Study MBGS205 by dose group:
  - o Percentage change in hip (total and femoral neck) bone mineral density measured by DEXA (g/cm^2) from Baseline in Study MBGS205 to Week 48 in Study MBGS206
  - o Percentage change in bone turnover markers (C-terminal telopeptide [CTx1], osteocalcin, bone alkaline phosphatase, and procollagen type 1 N-propeptide [P1NP]) from Baseline in Study MBGS205 to Week 48 in Study MBGS206
  - o Proportion of subjects with T-scores  $\leq$  -2.5 at Week 48
  - o Percentage change in bone density and bone biomarkers adjusted for vitamin D deficiency from Baseline in Study MBGS205 to Week 48 in Study MBGS206
  - o Change of oestradiol (absolute and percentage) from Baseline in Study MBGS205 to Week 48
  - o Proportion of subjects that overshoot testosterone (total testosterone above 1000 ng/dl [35 nmol/L], from first dose of study drug in Study MBGS205 until study completion)
  - o Change in PSA from Baseline in Study MBGS205 to Week 48 in Study MBGS206
  - o Change in haematocrit from Baseline in Study MBGS205 to Week 48 in Study MBGS206
  - o Change in blood pressure (systolic and diastolic) Baseline in Study MBGS205 to Week 48 in Study MBGS206
  - o Treatment emerged AE, SAE, and AESI (from first dose of study drug in Study MBGS205 until study completion)
  - o Relationship between change in bone mineral density from Baseline in Study MBGS205 to Week 48 in Study MBGS206 and absolute levels of oestradiol and total testosterone at Week 48 in MBGS206

2. In subjects that were randomized to placebo in Study MBGS205 by dose group:
  - o Percentage change in lumbar bone mineral density measured by DEXA (g/cm^2) from Baseline in Study MBGS206 to Week 48
  - o Percentage change in hip (total and femoral neck) bone mineral density measured by DEXA (g/cm^2) from Baseline in Study MBGS206 to Week 48
  - o Percentage change in bone turnover markers (CTx1, osteocalcin, bone alkaline phosphatase, and P1NP) from Baseline in Study MBGS206 to Week 48
  - o Change of oestradiol (absolute and percentage) from Baseline in Study MBGS206 to Week 48
  - o Proportion of subjects with T-scores  $\leq -2.5$  at Week 48 of Study MBGS206

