### 6.1 Intention-To-Treat population (ITT)

The ITT population includes all subjects who:

1. Are randomised, and
2. Receive at least one dose of MBGS206 study medication, and
3. Provide a baseline (see section 8.1.5 for full definition of baseline) primary endpoint safety value (lumbar spine) and at least 1 available evaluation of primary endpoint safety value (lumbar spine) post- Baseline in MBGS206.

Subjects will be analysed according to the treatment to which they were randomised.

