#### 8.1.1 Populations for analysis

Demographic and baseline characteristics will be summarised by Safety, Completers and ITT populations, unless otherwise stated.

Analyses of the primary endpoint and secondary safety BMD endpoints will be performed on ITT and completer population. Analysis of all other safety endpoints will use the safety population.

The secondary efficacy endpoints and exploratory endpoints will be analysed using the ITT population.

The safety and tolerability variables will be analysed using the Safety population.

PK data will be analysed using the PK population.

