### 8.6.3.4 Proportion of subjects that Overshoot Testosterone

The number and proportion of subjects that overshoot testosterone (total testosterone above 1000 ng/dL [35 nmol/L]) at each visit and at least once during the study will be summarised similar to that of Testosterone normalisation.

In addition the number and proportion of subjects whose maximum testosterone value falls into each of the below categories will be presented by visit and overall during the study:

- >1000 - <=1500ng/dl
- >1500 – <1800 ng/dL
- =>1800 - <= 2500 ng/dL
- >2500 ng/dL

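### The SAP gives conflicting analysis sets for testosterone overshoot, a safety endpoint; if ITT is the one used, men who stop before Week 36 are not counted

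*SAP*

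**What the plan says.** **Classification.** SAP 4.2.1 lists the endpoint as secondary safety: "Proportion of subjects that overshoot testosterone (total testosterone above 1000 ng/dl [35 nmol/L], from first dose of study drug". The count starts in MBGS205 for men on active drug there and in MBGS206 for former placebo men. Protocol 13.4.2.1 classifies it the same way. SAP 4.2.2, the list of secondary efficacy endpoints, does not include it.

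**Rules pointing to Safety.** SAP section 6 sends safety endpoints to the Safety population. SAP 8.1.1 gives the primary and BMD endpoints their own sets and then says "Analysis of all other safety endpoints will use the safety population". Protocol 13.5.3.1 places the summary of values above 1000 ng/dL in a section that uses the safety population.

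**Text pointing to ITT.** SAP 8.6.3 is headed as secondary efficacy and says "All analysis of secondary efficacy endpoints will be performed on the ITT population". Overshoot is subsection 8.6.3.4, where the counts "at each visit and at least once during the study will be summarised similar to that of Testosterone normalisation". Normalisation is an ITT analysis. Overshoot is also defined among the efficacy criteria (SAP 7.1.3.1), and it is absent from section 8.7, whose Safety-population rule covers the endpoints set out there.

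**What ITT requires.** Criterion 3 of SAP 6.1 needs a baseline lumbar value and "at least 1 available evaluation of primary endpoint safety value (lumbar spine") after baseline in MBGS206. For men who discontinue early, protocol Table 9-1, footnote 11, says the "EOT DEXA scan will be performed only if they reached minimum Week 36 (Visit 4) active treatment period". SAP 8.6.2 repeats that limit.

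**The concern.** A programmer working from 8.6.3.4 would find an ITT heading above it, a cross-reference to an ITT analysis and no override. By contrast, 8.6.2, which also sits in the efficacy chapter, names the safety population for the primary analysis. A programmer working from section 6 or 8.1.1 would use Safety. Both could claim to have followed the SAP.

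The choice is not neutral. Leaving before Week 36 removes a man from ITT, and one mandatory reason for stopping is testosterone of at least 1500 ng/dL at two consecutive visits (protocol 9.3.4). Every man stopped on that ground has overshot. Under ITT, a safety summary could therefore omit men whose treatment ended because of the very hormone level it describes. The rows for maximum testosterone above 1500 ng/dL are the most exposed.

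Two further facts make it worth settling in writing. SAP 3.2.3 has sponsor and CRO personnel unblinded when MBGS205 is unblinded, so an open choice of set could be made with allocation known. And SAP section 9, which lists changes from the protocol, mentions neither a change of set for overshoot nor the scan condition in ITT. The protocol's own ITT definition (13.3.1) asks only for a baseline and one later efficacy value.

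**Working it through.** **1. Who is lost under ITT.** Total testosterone is measured at Weeks 24, 28, 32, 36, 40, 44, 48 and 60 (protocol Table 9-1). The consecutive pairs that include an MBGS206 on-treatment visit and can trigger a stop before Week 36 are:

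- Weeks 24 and 28, for men continuing on active drug;
- Weeks 28 and 32, for all men. This is the first possible on-drug pair for former placebo men.

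If the result is acted on promptly, the man stops before Week 36, has no MBGS206 scan and fails ITT criterion 3. He stays in the Safety population, which needs only one MBGS206 dose (SAP 6.2). A pair ending at Week 36 or later leaves him eligible for the scan.

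**2. Which rows he belongs to.** At least 1500 ng/dL is above 1000, so he counts as an overshooter at least once. SAP 8.6.3.4 puts maxima above 1000 and up to 1500 in its first category and anything higher in the next three. Unless his maximum is exactly 1500, he belongs in one of the upper three.

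**3. The plan's own figure.** The synopsis has 30 entrants per previously active arm, about 17% dropout and approximately 25 completers. Check: 30 × (1 − 0.17) = 24.9, which agrees. The planned loss is thus about 5 men per arm, for any reason and at any time in the extension. Five before Week 36 is the upper end of what the plan assumes.

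**4. Size.** No overshoot rate is given, so the counts below are assumptions. In an arm of 30, let x men overshoot, m leave before Week 36, and k of those m be overshooters.

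- Safety: x/30
- ITT: (x − k)/(30 − m)

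| x | Safety | m | k | ITT |
|---|---|---|---|---|
| 6 | 20.0% | 2 | 1 | 5/28 = 17.9% |
| 6 | 20.0% | 3 | 2 | 4/27 = 14.8% |
| 6 | 20.0% | 5 | 3 | 3/25 = 12.0% |
| 6 | 20.0% | 5 | 5 | 1/25 = 4.0% |
| 6 | 20.0% | 5 | 0 | 6/25 = 24.0% |
| 3 | 10.0% | 5 | 3 | 0/25 = 0% |
| 3 | 10.0% | 5 | 0 | 3/25 = 12.0% |

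**5. Direction.** ITT gives the lower figure when k/m exceeds x/30, that is, when overshooters are over-represented among early leavers. With x = 6 and m = 5 the break-even is k = 1, since 5/25 = 20.0%. Stops under the testosterone criterion push k up; departures for unrelated reasons push the other way.

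**The case against.** The strongest reply is that the SAP, read literally, already answers the question. The ITT sentence in 8.6.3 is confined to secondary efficacy endpoints, overshoot is not on that list, and two general rules plus the protocol send it to Safety. Position within 8.6 does not fix the population, as the primary endpoint shows, and the comparison with normalisation may concern only the layout of the table. This stands to the extent that a reader might infer the SAP definitely analyses overshoot in ITT, and the documents do not support that. They support a conflict, with the loss of men conditional on following 8.6.3.

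A reader might also infer that men are taken off drug for overshoot. They are not: overshoot is above 1000 ng/dL, whereas stopping needs at least 1500 ng/dL twice in succession, and only a stop before Week 36 matters here.

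The numbers affected may be small or nil. Men who met MBGS205 discontinuation criteria cannot enter, and the earlier study in obese men with HH saw no peaks above the normal range (protocol 7.1.2), though it was small and lasted 12 weeks. Stopped men also remain visible in disposition, in listings and, where reported, in Safety-population tables of adverse events leading to discontinuation. An unblinded physician reviews testosterone at each visit, and all analyses are declared exploratory. These points limit the severity. They do not tell the programmer which set to use, nor make the overshoot table itself complete.

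Finally, the loss arises from the scan condition in ITT; without it, men with testosterone data who stop early would be kept. That is true, but naming the Safety population cures this endpoint whatever is done with ITT.

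**Conclusion.** The SAP is internally inconsistent on the analysis set for a secondary safety endpoint, and one of the two readings excludes everyone who stops before Week 36. That group includes any man stopped on the Week 24/28 or 28/32 pair, all of whom are overshooters and nearly all of whom belong in the upper maximum-testosterone categories.

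The size is unknown because no overshoot rate is given. With an assumed 6/30 (20%), ITT would report about 4% to 18% in the scenarios shown where overshooters are over-represented among early leavers, and 24% if the five early leavers are all non-overshooters. It would therefore go too far to say that ITT must understate the rate: the testosterone stopping criterion removes events, but other early departures can offset or reverse the effect. The range rests on 30 men per arm, at most five early leavers, and prompt action on the testosterone results.

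Severity: should-fix. The defect affects a safety summary and could be settled after unblinding, but it is a conflict rather than a definite misassignment, and the men concerned can be traced elsewhere in the report.

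**What to change.** State in 8.6.3.4, or move the subsection to 8.7 and state there, that the by-visit, at-least-once and maximum-testosterone summaries use the Safety population, with the at-least-once and maximum summaries taken over all scheduled values after the first dose of active drug. Restricting this to scheduled values keeps it consistent with SAP 8.1.7, under which unscheduled results are listed but not tabulated.

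No rule forcing stopped men into the numerator is needed. For the at-least-once summary they count already, because 1500 ng/dL exceeds 1000; for by-visit proportions such a rule would be wrong, since it would count them at visits where they have no high value.

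The cost is one SAP sentence and a population flag in the table program. No new data are required.

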#### 8.6.3.1 Testosterone Normalisation (Primary Definition)

The number and proportion of subjects with normal testosterone levels (testosterone value is between 300-1000 ng/dL inclusive) will be summarised by treatment regimen at each visit using the total testosterone assessed by ICON central lab. Observed values and LOCF values will be presented. In addition, a P-value for the comparison between each dose will be provided using Fisher's exact test.

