9 INVESTIGATIONAL PLAN

9.1 Overall Study Design and Plan

9.1.1 Description

This is a 6 month, active treatment, extension study, open to subjects who have completed the full 24 week treatment period in Study MBGS205 (a Phase IIb multicentre, double-blind, dose-ranging, randomised, placebo-controlled study evaluating safety and efficacy of BGS649 in male obese subjects with HH).

The main purpose of this study is to evaluate bone mineral density in subjects after 12 months exposure with BGS649. The study will also collect additional BGS649 safety and efficacy data on subjects that were randomised to placebo in Study MBGS205 and have 6 months active drug exposure in Study MBGS206. The study design and schedule of assessments are summarised in [Figure 9-1](#) and [Table 9-1](#), respectively.

Subjects that completed full 24 weeks treatment period of Study MBGS205 will be invited to participate. Informed consent will be taken prior to study procedures being performed. Study participation will comprise of the Extension Study Baseline visit (Week 24 of Study MBGS205), 7 visits during the treatment period up to Week 48 (End of Treatment [EOT]), and a Follow-Up (FU) visit for safety performed at Week 60, 12 weeks after the Week 48/EOT visit. The End of Study is defined as the last visit of the last global subject.

Extension Study Baseline assessment:

The Extension Study Baseline assessment will be performed on a same day as the EOT visit of Study MBGS205. As applicable, EOT assessments of Study MBGS205 will be used for Baseline assessments of Study MBGS206 and do not need to be repeated. The results of liver biochemistry, PSA, haematocrit, and electrocardiogram (ECG) assessments performed at the Baseline visit (EOT of MBGS205) may not be available for eligibility assessment, therefore results of these parameters from last valid visit of Study MBGS205 will be used to enable recruitment and dosing. This includes any of the parameters from last scheduled or unscheduled visit, measured not longer than 1 month before Baseline visit/EOT of MBGS205. Bone density from EOT assessment of MBGS205 will be used for eligibility evaluation for MBGS206.

If results of liver biochemistry, renal function, PSA, haematocrit and ECG measured at Extension Study Baseline visit/EOT of MBGS205 are subsequently found to meet any study discontinuation criteria, the subject will be withdrawn.

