## 3 STUDY DESIGN

### 3.1 General study design

This is a 6 month, active treatment, extension study, open to subjects who have completed the full 24 week treatment period in Study MBGS205 (a Phase IIb multicentre, double-blind, dose-ranging, randomised, placebo-controlled study evaluating safety and efficacy of BGS649 in male obese subjects with HH).

Study participation will comprise of the Extension Study Baseline visit (Week 24 of Study MBGS205, where the Extension Study Baseline assessment will be performed on a same day as the EOT visit of Study MBGS205), 7 visits during the treatment period up to Week 48 (End of Treatment [EOT]), and a Follow-Up (FU) visit for safety performed at Week 60, 12 weeks after the Week 48/EOT visit.

[figure not shown]
During the 24 week treatment period, subjects will take the required [REDACTED] time schedule of regular planned dose), starting with the first dose being taken at the baseline visit. The capsules will be taken orally by the subject with water. Subjects receiving active doses of BGS649 in Study MBGS205 will continue with the same dose in Study MBGS206; this transfer will be handled by the interactive response technology (IRT) and the blind will be maintained. Subjects receiving placebo in Study MBGS205 will be re-randomised on a 1:1:1 basis to each of the active treatment arms:

- o BGS649 [REDACTED] capsules)
- o BGS649 [REDACTED]
- o BGS649 [REDACTED] capsules).

The planned interim analysis of MBGS205 determined that all active doses met efficacy and safety criteria and therefore all three doses [REDACTED] were progressed into MBGS206.

Enrolment will continue until 30 subjects from each of the previous active treatment arms in Study MBGS205 have entered this study.

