## 7.2 Handling of missing data and outliers

### 7.2.1 Missing data analysis methods

Unless specified, data in summary tables will be presented using Observed Case (OC) data and therefore no missing data will be imputed.

For specified endpoints a last observation carried forward (LOCF) imputation will be utilised. In this approach subjects with a missing observed value at a visit will be imputed with the last non-missing, post-baseline value.

For each continuous exploratory endpoint, the change from Baseline will be assessed with a mixed model repeated measure (MMRM) analysis.

For data listings, unless specified, all data will be presented as they have been recorded (e.g. missing and partial dates will not be replaced).

---

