#### 8.1.3 Descriptive statistics

Continuous variables will be summarised using descriptive statistics including number of non-missing observations (n), arithmetic mean (Mean), median (Median), standard deviation (SD), minimum value (Min) , maximum value (Max) and number of missing observations (if any). One additional decimal point for mean and median and 2 additional decimal points for SD will be used.

For categorical variables, summaries will include the number of non-missing observations (n) or the number of patients in the population (N) as applicable, the counts of subjects and percentages. Percentages will be rounded to one decimal place. The number of missing values will be presented as a separate category with no percentage, but only if any missing value is recorded in the data for that summary.

Summary statistics will only be presented at each visit for which the parameter is scheduled to be

collected.

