#### 8.8.1.1 Testosterone Monitoring

To ensure adequate safety monitoring, serum total testosterone levels will be evaluated at each visit by an independent unblinded physician and if subject meets discontinuation criteria (total testosterone is  $\geq 1500$  ng/dL (52 nmol/L) at any 2 consecutive time points during the study), the subject will be discontinued from treatment. This would also include situation when first testosterone value that meets this threshold of  $\geq 1500$  ng/dL [52 nmol/L] was measured during MBGS205 and consecutive testosterone during study MBGS206.

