### 8.8.4 Sensitivity Analysis of Site 1156

To assess the impact of site 1156 on key endpoints the below analyses will be conducted utilising the modified populations (see section 6.0) which removes subjects enrolled from site 1156:

- Analysis of Proportion of Subject Achieving Normalisation of Total Testosterone (300-1000 ng/dl). Analysis will be conducted on the Central lab testosterone using LOCF imputation.
- Summary of Change in LH and FSH
- Summary of Vitals signs Parameters and Change from Baseline
- Summary of Blood Pressure Categorisation
- Summary of Body Composition

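### LOCF for testosterone normalisation has no end-of-treatment limit, so the Week 60 LOCF row mixes on-drug and off-drug values

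*SAP*

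**What the plan says.** Four statements combine.

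- **Which visits.** Under SAP 8.6.3.1 the number and proportion of men with normal testosterone "will be summarised by treatment regimen at each visit using the total testosterone assessed by ICON central lab". SAP 8.1.3 sets the general rule: "Summary statistics will only be presented at each visit for which the parameter is scheduled to be" collected.
- **Which data.** SAP 8.6.3.1 continues: "Observed values and LOCF values will be presented".
- **How gaps are filled.** Under SAP 7.2.1, "subjects with a missing observed value at a visit will be imputed with the last non-missing, post-baseline value". The rule names no last visit and does not refer to the end of treatment.
- **When testosterone is measured.** Protocol Table 9-1 marks total testosterone at Weeks 28 to 48 and again at the follow-up visit. SAP 8.8.1.1 agrees that "serum total testosterone levels will be evaluated at each visit by an independent unblinded physician". Protocol 9.1.1 describes the follow-up as a "visit for safety performed at Week 60, 12 weeks after the Week 48/EOT visit"; SAP 3.1 says the same. Treatment in this study lasts at most 24 weeks (Protocol synopsis), so Week 60 is off drug.

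SAP 8.6.3.2 analyses the secondary definition of normalisation in the same way. SAP 8.6.3.4 summarises overshoot along similar lines, without saying whether that includes LOCF. By contrast, the repeated-measures analysis of total testosterone in SAP 8.6.3.3 is confined to the period up to Week 48.

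**The concern.** Carrying a value forward across visits within the treatment period assumes that the level would have held under continued treatment. Carrying it across the end of treatment assumes that it holds after the drug is withdrawn, which is what an off-drug visit is there to observe. A Week 60 row built partly from treated values and partly from untreated ones estimates neither persistence after stopping nor response under continued treatment.

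If normalisation declines off drug, the error runs towards apparent persistence. A reader of the table could conclude that the effect outlasts treatment more than it does. If the overshoot table is also run with LOCF, values above 1000 ng/dL recorded on drug could likewise appear in an off-drug row. SAP 8.6.3.1 does not say at which visit, or on which version of the data, Fisher's test is run, so nothing in the text keeps a between-dose p-value away from this row.

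**Working it through.** **Does the text produce the result?** Normalisation is tabulated at each scheduled visit, Week 60 is a scheduled visit for total testosterone, LOCF is one of the two versions shown, and the LOCF rule has no end point. A completer who misses follow-up has the Week 48 sample as his last post-baseline value. A man who stops early should have an EOT visit within 7 days of stopping (Protocol 9.3.4), and that value is carried if he then misses follow-up. No passage in either document prevents this.

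**The plan's own figure.** The synopsis has 30 men entering per active arm and about 17% dropout: 30 × (1 − 0.17) = 24.9, which matches the stated target of about 25 completers. So about 5 men per arm are expected not to reach 48 weeks of total exposure. This figure concerns completion of treatment, not attendance at Week 60, and serves only as a guide to plausible missingness.

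**Inputs for the illustration**

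- n = 30 men per dose (Protocol synopsis and 13.1).
- m = 3 to 5 men without a Week 60 sample: assumption.
- p = 75% normal on drug: assumption, borrowed from the MBGS205 target in Protocol 7.1.2 and the reference value in Protocol 13.5.3.2.
- q = 10 to 40% truly normal at Week 60: assumption.
- The men who miss Week 60 have the same off-drug rate q as those who attend: assumption.

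**Formula.** Expected LOCF proportion at Week 60 = [(n − m) × q + m × p] / n. The inflation over the true rate is (m / n) × (p − q).

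| True off-drug rate q | LOCF, m = 3 | LOCF, m = 5 |
|---|---|---|
| 10% | 16.5% (+6.5 points) | 20.8% (+10.8 points) |
| 20% | 25.5% (+5.5 points) | 29.2% (+9.2 points) |
| 40% | 43.5% (+3.5 points) | 45.8% (+5.8 points) |

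The smallest value is 3/30 × (0.75 − 0.40) = 0.035. The largest is 5/30 × (0.75 − 0.10) = 0.108. If normalisation did not fall off drug (q = p), the inflation would be zero.

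**The case against.** Much of the case on the other side stands.

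- **Week 60 is not an endpoint.** Normalisation is defined at Week 48 (SAP 4.2.2), follow-up is a safety visit, and no objective or decision rule concerns persistence off drug. This stands and limits the importance of the point.
- **Observed values are printed alongside, only missing values are filled, and all analyses are exploratory.** This stands too. A careful reader could see the discrepancy.
- **The table shells are a separate document** (SAP 1) and may already stop LOCF at Week 48. That is possible, but the SAP is where the rule belongs.
- **LOCF does not always favour the drug.** A man withdrawn for two consecutive values of at least 1500 ng/dL may carry forward a value that counts as not normalised. This is true of individuals. The direction of the overall error depends on whether normalisation is less common off drug than on it.
- **The sizes are assumed.** They are. Men who stop early are still asked to attend follow-up, and the ITT definition (SAP 6.1) would make the denominator smaller than 30.

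A reader might also infer that LOCF inflates the Week 48 result by crediting men who stopped treatment. The documents do not support calling that an error. With 25 completers and 5 stoppers, all at 75%, the observed rate is 18.75/25 = 75% and the LOCF rate is 22.5/30 = 75%. A lower figure, 18.75/30 = 62.5%, appears only if stoppers are counted as failures, which is a choice of estimand that neither document makes. Few such men should arise in any case. ITT requires a lumbar scan in MBGS206, the scan is done only in men who reached Week 36, and stoppers should have a testosterone sample at their own EOT visit.

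Nor is the site 1156 check in SAP 8.8.4 defective because "Analysis will be conducted on the Central lab testosterone using LOCF imputation". It compares like with like against one of the two main versions, and an observed-case version would be optional.

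**Conclusion.** The point holds for Week 60, and its severity is minor. As written, SAP 7.2.1 and 8.6.3.1 place on-drug values in an off-drug row for any man without a Week 60 sample. The same holds for the secondary definition in 8.6.3.2 and possibly for overshoot in 8.6.3.4. The row overstates persistence if normalisation declines after treatment. An inflation of 3.5 to 10.8 points is an illustration that rests on assumed rates and missingness, not an estimate for this trial. It does not follow that the Week 48 endpoint is biased or that the site 1156 analysis is unsound.

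**What to change.** State in SAP 7.2.1 and 8.6.3.1 that LOCF is applied only through Week 48/EOT, and present Week 60 as observed values only. SAP 8.6.3.2 then follows without further change. SAP 8.6.3.4 should say whether overshoot is summarised with LOCF and, if so, apply the same limit. A separate count of men who stopped treatment before Week 48 would help readers of the Week 48 row but is optional.

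The cost is a few sentences and minor programming, with no new data. The downside is a smaller Week 60 denominator, which should be printed with the row.
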